To keep the blind during the study, stratification factors will be entered for all patients at Extension Week 0. In the case there were no EULAR-CRP response status available at week 40, the last EULAR-CRP response status assessment done between Weeks 40 and 48 will be used. Baseline values for assessment of EULAR-CRP will be the last value from screening to Day 0 (Week 0) of the study. A schematic of the study patient assignment for this randomization is presented in Figure 3.

Patients, who are assigned to receive CT-P10 with their first infusion in the study, will be considered as group 1 and maintain CT-P10 for the third course.

Patients, who are assigned to receive Rituxan with their first infusion in the study, will be randomized 1:1 ratio to group 2 (CT-P10 will be administered for the third course) and group 3 (Rituxan will be maintained for the third course) at Extension Week 0.

Patients, who are assigned to receive MabThera with their first infusion in the study, will be considered as group 4 and receive CT-P10 for the third course at Extension Week 0.

The third course of treatment will be initiated between Week 48 and Week 52 of the Entire Study Period if patients become eligible according to the predefined safety criteria for the Protocol Version 5.1, including Country-Specific Protocol Amendment 1 (US) – 01 April 2016 Page 33 course based on the results assessed within 8 weeks from the Extension Week 0. A visit window is not permitted on the day of second infusion for the third course of treatment (study drug may continue after discussion with the sponsor if a deviation occurs).

Unscheduled visit(s) can be conducted for assessment of safety criteria until the initiation of the third course of treatment.

For patients who receive the third course of treatment at Week 48, the scheduled assessments and samplings should be performed according to the schedule of events and sampling schemes for the Extension Week 0 provided in the Table 6 and Table 9, respectively. Otherwise, all scheduled assessments for Week 48 should be performed separately from the Extension Week 0 according to the schedule of events (Table 6).

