All patients will receive MTX and folic acid concomitantly. Each patient may receive 3 courses of treatment; the first course will be an infusion of study drug (CT-P10, Rituxan or MabThera) at Week 0 and Week 2. If patients meet the predefined safety criteria, patients are eligible to receive the additional course(s) of study drug (2 infusions in each course of 2-week interval) at the discretion of the investigator. For the second course of treatment in the Main Study Period, patients, who do not meet the predefined safety criteria, will not receive an additional course of treatment, but they will be followed according to the schedule of events (Table 5) for the Main Study Period.

For the third course of treatment in the Extension Study Period, patients, who do not meet the predefined safety criteria within the time frame for the study drug infusion, will not receive an additional course of treatment and will be terminated from the study.

Safety criteria for the any courses of treatment after the first course are predefined as:

- Absolute neutrophil count should be $\geq 1.5 \times 10^3$ cells/µL (SI units: $\geq 1.5 \times 10^9$ cells/L), platelet count should be $\geq 75 \times 10^3$ cells/µL (SI units: $\geq 75 \times 10^9$ cells/L), asparatate aminotransferase or alanine aminotransferase should be ≤ 2.5 times upper limit of normal and levels of IgG should be ≥ 500 mg/dL (5.0g/L), at the last blood sample analysis (i.e, Week 16 for second course of treatment and within 8 weeks from the Extension Week 0 for third course of treatment).
- The patient has not developed any conditions which, in the investigators opinion, would preclude the patient receiving further courses of treatment (e.g., any new or uncontrolled disease such as, but not limited to, cardiovascular disease, or nervous system, pulmonary, renal, hepatic, endocrine or gastrointestinal disorder).

For the Main Study Period, a schedule of events for patients who receive both first and second courses of treatment (from Screening to Week 48 or End-of-Study Visit) is provided in Table 4 and a schedule of events for the patients who do not receive the second course of treatment (from Week 24 to Week 48 or End-of-Study Visit) is provided in Table 5. For the Extension Study Period, a schedule of events for patients is provided in Table 6.

A patient will be considered as having completed the study if:

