 - Neutrophil count $\geq 1.5 \times 10^3$ cells/µL (SI units: $\geq 1.5 \times 10^9$ cells/L)
 - Platelet count $\geq 75 \times 10^3$ cells/µL (SI units: $\geq 75 \times 10^9$ cells/L)
- 8. Patient has adequate renal and hepatic function at Screening as defined by the following clinical chemistry results:
 - Serum creatinine <1.5 × upper limit of normal (ULN) or an estimated creatinine clearance level >50 mL/min (by Cockcroft-Gault formula)
 - Serum alanine aminotransferase <2.5 × ULN
 - Serum aspartate aminotransferase $<2.5 \times ULN$
 - Serum total bilirubin $< 2 \times ULN$
- 9. Patient has the ability to comprehend the full nature and purpose of the study, including possible risks and side effects, to cooperate with the investigator, to understand verbal and/or written instructions, and to comply with the requirements of the entire study.

- 10. Patient (or legal guardian, if applicable) has been informed of the full nature and purpose of the study, including possible risks and side effects, and given ample time and opportunity to read and understand this information, and provide signed and dated written informed consent before inclusion in the study.
- 11. For both male and female patients, the patient and their partners of childbearing potential either agree to practice total abstinence or use 2 of the following medically acceptable methods of contraception during the course of the study and for 12 months following discontinuation of study drug (excluding women who are not of childbearing potential and men who have been sterilized):
 - Barrier contraceptives (male condom, female condom, or diaphragm with a spermicidal gel)
 - Hormonal contraceptives (implants, injectables, combination oral contraceptives, transdermal patches, or contraceptive rings)
 - Intrauterine device

Male and female patients and their partners who have been surgically sterilized for less than 6 months prior to the date of informed consent must agree to use 2 medically acceptable methods of contraception or to practice total abstinence.

Menopausal females must have experienced their last period more than 12 months prior to the date of informed consent to be classified as not of childbearing.

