**Figure 1: Study Schematic**

\* The third course of treatment will be initiated between Week 48 and Week 52 of the Entire Study Period based on the results assessed within 8 weeks from the Extension Week 0.

Any courses of treatment after the first course will be initiated if the following safety criteria are met:

- Absolute neutrophil count should be  $\geq 1.5 \times 10^3$  cells/ $\mu$ L (SI units:  $\geq 1.5 \times 10^9$  cells/L), platelet count should be  $\geq 75 \times 10^3$  cells/ $\mu$ L (SI units:  $\geq 75 \times 10^9$  cells/L), aspartate aminotransferase or alanine aminotransferase should be  $\leq 2.5$  times the upper limit of normal and levels of IgG should be  $\geq 500$  mg/dL (5.0 g/L), at the last blood sample analysis (i.e. Week 16 for second course of treatment and within 8 Weeks from the Extension Week 0 for third course of treatment).
- The patient has not developed any conditions which, in the investigators opinion, would preclude the patient receiving further courses of treatment (e.g., any new or uncontrolled disease such as, but not limited to, cardiovascular disease, or nervous system, pulmonary, renal, hepatic, endocrine, or gastrointestinal disorder).

[figure not shown]
Note that Part 1 and Part 2 of the study will follow the study schematic specified in [Figure 1](#).

In Part 1, the first approximately 189 patients with RA will be randomly assigned in a 1:1:1 ratio to 1 of 3 treatment groups, CT-P10, Rituxan, or MabThera (approximately 63 patients per treatment group).

In Part 2, approximately 172 subsequent patients with RA will be randomly assigned in a 1:1 ratio to 1 of 2 treatment groups, CT-P10 or Rituxan. In total, approximately 361 patients will be available for analysis.

Approximately 189 initial patients to be enrolled in the study will be assigned to Part 1 and all subsequent patients enrolled in the study will be assigned to Part 2. All patients from Part 1 of the study will be included in Part 2 of the study and undergo all assessments performed in Part 2. A schematic of study patient assignment for Part 1 and Part 2 is presented in [Figure 2](#). Part 2 will run independently and in parallel with Part 1.

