**APPENDIX 2: Table of CTCAE Terms and Grades**

CTCAE Term	Laboratory Parameter	Level	Grade 1	Grade 2	Grade 3	Grade 4
Anemia	Hemoglobin	Low	<LLN - 10.0 g/dL; <LLN - 100 g/L	<10.0 - 8.0 g/dL; <100 - 80g/L	<8.0 g/dL; <80 g/L;	-
Alanine aminotransferase increased	Alanine Aminotransferase (ALT)	High	>ULN - 3.0 x ULN	>3.0 - 5.0 x ULN	>5.0 - 20.0 x ULN	>20.0 x ULN
Alkaline phosphatase increased	Alkaline phosphatase	High	>ULN - 2.5 x ULN	>2.5 - 5.0 x ULN	>5.0 - 20.0 x ULN	>20.0 x ULN
Aspartate aminotransferase increased	Aspartate Aminotransferase (AST)	High	>ULN - 3.0 x ULN	>3.0 - 5.0 x ULN	>5.0 - 20.0 x ULN	>20.0 x ULN
Blood bilirubin increased	Total Bilirubin	High	>ULN - 1.5 x ULN	>1.5 - 3.0 x ULN	>3.0 - 10.0 x ULN	>10.0 x ULN
Chronic kidney disease	Creatinine Clearance (Est by Weight)	Low	<LLN - 60 ml/min	<60 - 30 ml/min	<30 - 15 ml/min	<15 ml/min

CPK increased	Creatine Phosphokinase (CPK)	High	>ULN - 2.5 x ULN	>2.5 x ULN - 5 x ULN	>5 x ULN - 10 x ULN	>10 x ULN
Creatinine increased	Creatinine	High	>1 - 1.5 x baseline; >ULN - 1.5 x ULN	>1.5 - 3.0 x baseline; >1.5 - 3.0 x ULN	>3.0 baseline; >3.0 - 6.0 x ULN	>6.0 x ULN
GGT increased	Gamma Glutamyl Transferase	High	>ULN - 2.5 x ULN	>2.5 - 5.0 x ULN	>5.0 - 20.0 x ULN	>20.0 x ULN
Hemoglobin increased	Hemoglobin	High	Increase in >0 - 2 gm/dL above ULN or above baseline if baseline is above ULN	Increase in >2 - 4 gm/dL above ULN or above baseline if baseline is above ULN	Increase in >4 gm/dL above ULN or above baseline if baseline is above ULN	-
Hypercalcemia	Calcium	High	>ULN - 11.5 mg/dL; >ULN - 2.9 mmol/L	>11.5 - 12.5 mg/dL; >2.9 - 3.1 mmol/L	>12.5 - 13.5 mg/dL; >3.1 - 3.4 mmol/L	>13.5 mg/dL; >3.4 mmol/L
Hyperkalemia	Potassium	High	>ULN - 5.5 mmol/L	>5.5 - 6.0 mmol/L	>6.0 - 7.0 mmol/L	>7.0 mmol/L

Hypernatremia	Sodium	High	>ULN - 150 mmol/L	>150 - 155 mmol/L	>155 - 160 mmol/L;	>160 mmol/L
Hypoalbuminemia	Albumin	Low	<LLN - 3 g/dL; <LLN - 30 g/L	<3 - 2 g/dL; <30 - 20 g/L	<2 g/dL; <20 g/L	-
Hypocalcemia	Calcium	Low	<LLN - 8.0 mg/dL; <LLN - 2.0 mmol/L	<8.0 - 7.0 mg/dL; <2.0 - 1.75 mmol/L	<7.0 - 6.0 mg/dL; <1.75 - 1.5 mmol/L	<6.0 mg/dL; <1.5 mmol/L
Hypoglycemia	Glucose	Low	<LLN - 55 mg/dL; <LLN - 3.0 mmol/L	<55 - 40 mg/dL; <3.0 - 2.2 mmol/L	<40 - 30 mg/dL; <2.2 - 1.7 mmol/L	<30 mg/dL; <1.7 mmol/L
Hypokalemia	Potassium	Low	<LLN - 3.0 mmol/L	<LLN - 3.0 mmol/L	<3.0 - 2.5 mmol/L	<2.5 mmol/L
Hyponatremia	Sodium	Low	<LLN - 130 mmol/L		<130 - 120 mmol/L	<120 mmol/L

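### The retreatment criteria require AST *or* ALT to be within 2.5 × ULN, so read literally one normal enzyme satisfies the only numeric liver limit for courses 2 and 3

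*Protocol*

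**What the plan says.** Protocol Section 3.1 sets safety criteria that a patient must meet before a second or third course. The laboratory bullet covers neutrophils, platelets, transaminases and IgG. Its transaminase item reads "asparatate aminotransferase or alanine aminotransferase should be" no more than 2.5 × ULN, and the item is then joined to the IgG limit by *and*. The sample that counts is Week 16 for course 2, and one taken within 8 weeks of Extension Week 0 for course 3.

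The clause appears four times: in the synopsis, in the note to Figure 1 in Section 3.1, again in the body of Section 3.1, and in SAP Section 4.1 under Figure 1 ("aspartate aminotransferase or alanine aminotransferase should be"). Nothing elsewhere in either document says that both enzymes must meet the limit.

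The second bullet of the same criteria excludes patients with a new condition that, "in the investigators opinion, would preclude the patient receiving further courses of treatment"; hepatic disorder is among the examples. Section 3.1 also leaves further courses to the investigator's discretion.

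At entry, inclusion criterion 8 (Section 4.1.1) lists the enzymes on separate lines: "Serum alanine aminotransferase <2.5 × ULN" and, on the next line, "Serum aspartate aminotransferase" with the same bound.

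**The concern.** The item is a condition to be met before dosing. When two tests are joined by *or* in such a condition, meeting one is enough. On that reading the clause stops a course only if both enzymes are above 2.5 × ULN, and one normal value passes the patient however high the other is.

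This is the only numeric hepatic limit for courses 2 and 3, because bilirubin is not on the retreatment list. All patients also take methotrexate, for which Section 5.7 names significantly impaired hepatic function as a contraindication. Section 6.5.8 allows enrolment of patients who are positive for hepatitis B core immunoglobulin but negative for hepatitis B DNA. The limit should therefore work for each enzyme.

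Two things are at stake. Where a site follows the literal text, withholding a dose from a patient with one markedly raised enzyme rests on individual judgement alone. And sites that read the clause differently would apply different limits, with no written rule to show which is right. The retreatment list is lighter than the entry list in other ways too (it has no hemoglobin, white cell count, creatinine or bilirubin), and that is not the complaint. The complaint is that the one transaminase limit it does set does not bind each enzyme.

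**Working it through.** The plan gives no figure to reproduce here. The check is a logical one, followed by an illustrative count.

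**Step 1. Enumerate the cases.** Classify each enzyme at the deciding sample as within the limit (≤ 2.5 × ULN) or above it.

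| AST | ALT | As written (*or*) | Each enzyme required |
|---|---|---|---|
| within | within | pass | pass |
| above | within | pass | fail |
| within | above | pass | fail |
| above | above | fail | fail |

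The literal rule blocks 1 of the 4 combinations; a rule on each enzyme blocks 3 of 4. They disagree in exactly two, those with one enzyme raised. These are logical cases and not patient frequencies.

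**Step 2. Put a value in.** Take ALT 8 × ULN and AST 2 × ULN. AST is within 2.5 × ULN, so the clause is met. Under "Alanine aminotransferase increased", SAP Appendix 2 assigns Grade 3 to values above 5.0 and up to 20.0 × ULN, so this ALT is Grade 3.

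**Step 3. See how the protocol uses *or* elsewhere.** The renal part of inclusion criterion 8 sets creatinine below 1.5 × "upper limit of normal (ULN) or an estimated creatinine clearance level" above 50 mL/min; either one suffices. The active-disease criterion (inclusion criterion 3) accepts CRP or ESR in the same way. Where the protocol wants both transaminases within bounds, at entry, it lists them separately. A site following this usage would reach the permissive reading.

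**Step 4. Gauge the number of patients.** The documents give no rate of isolated transaminase elevation. Assume a proportion p of the 322 patients expected to be evaluable (Protocol Section 7.5) have exactly one enzyme above the limit at Week 16. The expected number is 322 × p:

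- p = 0.5%: 322 × 0.005 = 1.6
- p = 1%: 322 × 0.01 = 3.2
- p = 2%: 322 × 0.02 = 6.4
- p = 3%: 322 × 0.03 = 9.7

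That is about 2 to 10 patients for whom the two readings give different answers at the course 2 decision.

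**Step 5. Effect on the primary analysis.** Table 4, footnote 5, places the Week 24 assessments before the Week 24 infusion. The clause governs only later dosing, so the Week 24 primary efficacy analysis does not depend on it.

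**The case against.** The best defence is that the clause is ambiguous and not mistaken. It applies one shared ceiling to two named enzymes within a list of safety limits, and a clinician may well read it as saying that neither may exceed the ceiling. The creatinine and CRP/ESR examples are not exact parallels, because each joins two complete tests with their own thresholds. The protocol is also loose with connectors elsewhere, and nothing shows that any site read the clause permissively. Much of this stands: the intended meaning probably was that neither enzyme may exceed the limit. But that is a reason to write it. As worded, the clause does not say so, and retreating a patient with one very high enzyme would breach no numeric criterion.

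The second argument is that other safeguards would catch a serious case: the second bullet, investigator discretion, the methotrexate contraindication (Section 5.7), withdrawal for an adverse event that compromises safety (Section 4.2.1), extra blood samples if hepatic symptoms are suspected (Section 6.6.3) and the DSMB (Section 10.1.1). These are real and lower the risk, most of all for an extreme value such as the Grade 3 example. None sets a transaminase threshold, so none repairs the clause or makes sites uniform.

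The third is that the patient count is weak, and this is fair. The rate is assumed, 322 is the expected number evaluable for efficacy and not the number facing a course 2 decision, and a patient would actually be dosed differently only if the site read the clause permissively and the investigator chose to treat. The count shows scale only.

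**Conclusion.** The concern holds. Read literally, the transaminase item fails only when both enzymes exceed 2.5 × ULN, it says so in all four places, and no other text corrects it. It does not do what a limit on each enzyme should do.

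This is a patient-safety wording correction that should be made; it does not threaten the validity of the trial. The logical result rests on the text alone. The figure of about 2 to 10 patients rests on an assumed rate of 0.5% to 3% applied to 322, and counts patients classified differently, not patients harmed.

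**What to change.** In the synopsis, both places in Protocol Section 3.1 and SAP Section 4.1, replace the clause with: *AST and ALT must each be ≤ 2.5 × ULN*. Send sites a clarification letter with the amendment.

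Both enzymes are already in the chemistry panel, so no tests are added. The cost falls on the few patients with one raised enzyme:

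- **Course 2.** They would not be retreated but would stay in follow-up under Table 5. The decision uses the Week 16 sample, and the re-assessment provision is written for the third course, so a transient rise at Week 16 would rule out course 2. If the sponsor thinks that too strict, a retest before Week 24 could be added in the same amendment.
- **Course 3.** Patients still above the limit when the infusion window closes would be terminated from the study. The protocol already provides for this: "Unscheduled visit(s) can be conducted for assessment of safety criteria until the initiation of the third course of treatment".

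The amendment needs IRB/IEC approval (Section 10.2.1) across approximately 110 centers (Section 4.1).

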dendritic cell function may remain impaired beyond the recovery of B-cells following B-cell depletion (Toubi et al 2007; Youinou et al 2007). Cellular interactions, such as antigen processing and presentation, occur upstream of the proinflammatory cytokine response involving tumor necrosis factor (TNF)-alpha (TNF- α), interleukin-1 (IL-1), and interleukin-6. In addition, production of immunoglobulin M (IgM)-RF and IgG-RF by plasma cells in the rheumatoid synovium may act as a self-perpetuating stimulus for local B-cell proliferation and differentiation (Edwards 1999). Therefore, it appears increasingly evident that B-cells play a key pathogenetic role in the induction and maintenance of RA.

Clinical relevance of depleting B-cells in RA has been demonstrated by using a cytotoxic, chimeric anti-CD20 monoclonal antibody (Rituxan and MabThera) and these products have been approved for the treatment of patients with RA who have an inadequate response to TNF- α blocking agents. Also, previous studies on anti-TNF- α naïve patients with RA who did not benefit from methotrexate (MTX) therapy show that two-thirds of these patients obtained a clinical response following anti-CD20 therapy as measured by the American College of Rheumatology (ACR) 20% improvement criteria (ACR20) (Emery et al 2006). However, the adverse event (AE) profile included a high frequency of infusion-related events requiring premedication with intravenous (IV) steroids. One hypothesis is that rapid B-cell lysis is the driver for the observed in up to 25% of patients treated with a chimeric anti-CD20 antibody (Higashida et al 2005).

Following initial treatment, patients typically remain B-cell depleted for between 6 and 12 months, and some patients show no B-cell recovery for longer periods (MabThera 2015; Rituxan 2014). Currently, retreatment is given upon disease relapse, indicating that patients do not keep their initial clinical benefit over time. Also, in patients who initially do not respond to treatment, the prolonged B-cell depletion presents a risk without clinical benefit.

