3.1 Study Design

This is a randomized, controlled, multicenter, 3-arm, parallel-group, double-blind, prospective, PK, efficacy, PD, and safety Phase 3 study. There will be up to 3 periods in this study:

- Screening Period:
 - Week -6 through Week 0 (Day -42 to Day -1)
- Study Periods:
 - Main Study Period: Week 0 through Week 48 of the Study Period (Day 0 to Day 336)
 - Extension Study Period: Extension Week 0 through Week 24 (Extension Day 0 to Day 168)

The study duration will be up to 76 weeks after the Week 0 infusion. Extension Study Period will be initiated between Week 48 and Week 52 of the Entire Study Period. A schematic of the study design is presented in Figure 1. There will be additional follow-up visits for patients with B-cell, IgM and IgG values below the lower limit or normal (LLN) or less than 50% of their baseline value until recovery is achieved for one of them.

The term "Extension" will be used for all the visits in the Extension Study Period (i.e. Extension Week X or Extension Day X). Otherwise, visits will simply be stated as Week X.

* The third course of treatment will be initiated between Week 48 and Week 52 of the Entire Study Period based on the results assessed within 8 weeks from the Extension Week 0.

*Any courses of treatment after the first course of treatment will be initiated if the following safety criteria are met:

- Absolute neutrophil count should be ≥1.5 × 10³ cells/µL (SI units: ≥1.5 × 10⁹ cells/L), platelet count should be ≥75 × 10³ cells/µL (SI units: ≥75 × 10⁹ cells/L), asparatate aminotransferase or alanine aminotransferase should be ≤ 2.5 times upper limit of normal and levels of IgG should be ≥ 500 mg/dL (5.0g/L), at the last blood sample analysis (i.e, Week 16 for second course of treatment and within 8 weeks from the Extension Week 0 for third course of treatment)
- The patient has not developed any conditions which, in the investigators opinion, would preclude the patient receiving further courses of treatment (e.g., any new or uncontrolled disease such as, but not limited to, cardiovascular disease, or nervous system, pulmonary, renal, hepatic, endocrine or gastrointestinal disorder).

Note: Part 1 and Part 2 of the study will follow this study scheme.

In Part 1, the first approximately 189 patients with RA will be randomly assigned in a 1:1:1 ratio to 1 of 3 treatment groups, CT-P10, Rituxan or MabThera (approximately 63 patients per treatment group).

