- A patient who does not continue on the Extension Study Period and completes all visits up to Week 48
- A patient who continue on the Extension Study Period and completes all visits up to Extension Week 24

Discontinuation is defined as early discontinuation for any reason. These patients, if possible, should have an End-of-Study Visit.

Study termination is defined as the date on which the last patient completes the last visit (if the study is not discontinued by CELLTRION, Inc.).

Patients with B-cell, IgM and IgG values below the LLN or less than 50% of their baseline value should be monitored every 8 weeks after the study completion until recovery is achieved for one of them (equal to or higher than the LLN OR at least 50% of the baseline value). Upon the study completion, additional follow-up of B-cell, IgM and IgG will be determined by the Data Safety Monitoring Board (DSMB).

4 Patient Selection and Withdrawal Criteria

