6.3.1 B-cells

Blood samples for B-cell kinetics (central laboratory) will be obtained from each patient during the Study Periods.

Patients with B-cell, IgM and IgG values below the LLN or less than 50% of their baseline value should be monitored every 8 weeks after the study completion until recovery is achieved for one of them (equal to or higher than the lower limit of normal OR at least 50% of the baseline value). Upon the study completion, additional follow-up of B-cell, IgM and IgG monitoring will be determined by the DSMB.

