- 9. All scheduled 12-lead electrocardiograms (ECG) must be performed after the patient has rested quietly for at least 5 minutes in the supine position. On the day of infusion, 12-lead ECGs will be also performed after 1 hour (±15 minutes) after the end of the study drug infusion for the hypersensitivity monitoring. At Extension Week 0, 12-lead ECG will be performed prior to study drug infusion. If Extension Week 0 is conducted on the same day with Week 48, assessment result of 12-lead ECG performed prior to study drug infusion will be used for the ECG assessment to be performed at Week 48.
- 10. Additional vital signs including blood pressure, heart and respiratory rates, and body temperature (before administration [within 15 minutes prior to the beginning of the study drug infusion], within 15 minutes after the end of the study drug infusion, and at 1 hour [±15 minutes] after the end of the study drug infusion) will be assessed to monitor for possible hypersensitivity reactions. In addition, hypersensitivity should be monitored by routine continuous clinical monitoring including ECG (12-lead) monitoring 1 hour (±15 minutes) after the end of the study drug infusion. Emergency equipment and medication, such as adrenaline, antihistamines, corticosteroids, and respiratory support including inhalational therapy, oxygen, and artificial ventilator must be available.
- 11. ACR20, ACR50, ACR70, and hybrid ACR will be calculated from these assessments. It is recommended that the joint count assessments are performed by the same physician when possible.
- 12. Twenty eight tender and swollen joints, ESR or CRP, and patient's general health or global disease activity measured on VAS will be assessed for DAS28 calculation. The European League Against Rheumatism response criteria will be derived from the DAS28.
- 13. Patients with B-cell, IgM and IgG values below the LLN or less than 50% of their baseline value of Main Study Period should be monitored every 8 weeks (±14 days) after the study completion until recovery is achieved for one of them (equal to or higher than the lower limit of normal OR at least 50% of the baseline value of Main Study Period). Upon the study completion, additional follow-up of B-cell, IgM and IgG monitoring will be determined by the Data Safety Monitoring Board (DSMB).

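### The post-study B-cell, IgM and IgG follow-up rule contradicts itself: any value between the LLN and half of baseline meets the start and stop conditions together, and what must recover is unclear

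*Protocol*

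**What the plan says.** Start (Protocol Section 3.1, applying once the study is complete): "Patients with B-cell, IgM and IgG values below the LLN or less than 50% of their baseline value should be monitored every 8 weeks".

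Stop (same paragraph): "until recovery is achieved for one of them (equal to or higher than the LLN OR at least 50% of the baseline value".

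DSMB (next sentence): "additional follow-up of B-cell, IgM and IgG will be determined by the Data Safety Monitoring Board (DSMB". Section 6.3.1 repeats this: "Upon the study completion, additional follow-up of B-cell, IgM and IgG monitoring will be determined by the DSMB". No criterion is given for that decision.

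The rule is repeated in these places:

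- **Full rule, Protocol:** Section 6.3.1 and Section 12.1 (Table 4 footnote 16, Table 5 footnote 12, Table 6 footnote 13). The footnotes write out the LLN: "until recovery is achieved for one of them (equal to or higher than the lower limit of normal OR at least 50% of the baseline". Table 6 adds only a ±14-day window and specifies the Main Study Period baseline.
- **Full rule, SAP:** Appendix 1, footnotes 16, 12 and 13 of the three schedules of events.
- **Short form:** the Study Design part of the Protocol synopsis, the opening of Section 3.1 and SAP Section 4.1. For example: "or less than 50% of their baseline value until recovery is achieved for one of them".

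No passage says that recovery is judged on the criterion that started monitoring, or that all three markers must recover. Neither document defines recovery in any other way.

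**The concern.** Start is *A or B*. For stop to be its opposite, it would have to be *not A and not B*. The text instead gives *not A or not B*, so a single result can place a patient in follow-up and discharge that patient at the same time. The phrase *one of them* adds a second problem, because it can refer to one of the three markers or to one of the two criteria.

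This matters because depletion can outlast the last visit. Protocol Section 1 says that "patients typically remain B-cell depleted for between 6 and 12 months, and some patients show no B-cell recovery for longer periods". After a third course, the last infusion is at Extension Week 2 and the last visit at Extension Week 24, which is 24 − 2 = 22 weeks. A patient who finishes at Week 48 after a second course has 48 − 26 = 22 weeks. Under Section 6.5.10.3, only serious adverse drug reactions are reported after the last assessment. The 8-weekly rule is therefore the only routine laboratory monitoring mandated after completion. Section 7.8.6 also makes the second clinical study report wait until this follow-up is closed. Sites that read the rule differently would close similar patients at different times.

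**Working it through.** This is a logic check. The plan gives no figure to reproduce.

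**Inputs.** The start and stop rules come from Protocol Section 3.1. Neither document gives an LLN for IgG, IgM or B cells; the note to SAP Appendix 2 refers only to central-laboratory ranges. The IgG LLNs below are assumptions, tried over 500 to 800 mg/dL.

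**Step 1: one marker.** Let A be *value < LLN* and B be *value < 0.5 × baseline*. Start = A or B. Stop = not A or not B.

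| State | A | B | Start met | Stop met |
|---|---|---|---|---|
| Neither | no | no | no | yes |
| Below LLN only | yes | no | yes | yes |
| Below half of baseline only | no | yes | yes | yes |
| Both | yes | yes | yes | no |

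Of the three states that start monitoring, two already satisfy the stop rule. The overlap runs from min(LLN, 0.5 × baseline) up to, but not including, the larger of the two. It is empty only when LLN = 0.5 × baseline.

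**Step 2: IgG illustrations (mg/dL, whole numbers).**

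| Assumed LLN | Baseline | 0.5 × baseline | Values meeting start and stop |
|---|---|---|---|
| 700 | 1,000 | 500 | 500 to 699 |
| 700 | 850 | 425 | 425 to 699 |
| 600 | 1,600 | 800 | 600 to 799 |
| 600 | 1,200 | 600 | none |

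The overlap occurs whether half of baseline lies below or above the LLN.

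**Step 3: three markers.** Each marker has four states, so there are 4³ = 64 patterns.

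| Reading of *one of them* | Any low marker starts monitoring | All three must be low to start |
|---|---|---|
| One marker | 62 of 63 also meet stop | 26 of 27 |
| One criterion, required of every low marker | 26 of 63 | 8 of 27 |

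The counts arise as follows:

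- **Any low marker:** 64 − 1 = 63 patterns start monitoring. On the marker reading, only the pattern with all three markers failing both criteria is retained, leaving 62. Of these, 36 contain a marker failing both: 64 − 3³ = 37 patterns contain one, less the retained pattern.
- **All three low:** 3³ = 27 patterns start and 26 also stop. Of these 26, 18 contain a marker failing both (27 − 2³ − 1).
- **Criterion reading:** the patterns released are those with no marker failing both, 3³ − 1 = 26 and 2³ = 8.

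These count logical patterns. They are not patient proportions.

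**The case against.** The strongest reply is that the intent is easy to guess: judge recovery on whichever criterion started monitoring, and let the DSMB extend follow-up where needed. That reading would remove the same-value overlap, but neither document states it, and it would not settle whether one marker's recovery ends follow-up of the others. The DSMB point does stand in part. The sentence concerns additional follow-up and can be read as a backstop, so a reader who infers two competing deciders goes further than the text. Equally, leaving mandated monitoring does not mean leaving all follow-up.

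A second reply also stands. The OR in the stop rule may serve patients whose baseline is already below the LLN. Protocol Section 4.1.1 sets no IgG, IgM or B-cell minimum at entry, so such patients can exist. If the stop rule were made the exact opposite of the start rule with the present thresholds, they could leave only by rising above their own baseline, and follow-up might be open-ended.

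Four stronger inferences are tempting but not supported:

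- **The B-cell endpoint is truncated or records false recoveries.** SAP Section 12.1 summarises B-cell counts only to Extension Week 24, and Section 12.2 models them only to Week 24. SAP Section 5 limits visit summaries to scheduled visits unless otherwise stated, and no recovery variable is defined. SAP Section 13.2 reports immunoglobulins under the LLN directly.
- **The rule conflicts with the IgG floor.** The requirement that "levels of IgG should be ≥ 500 mg/dL (5.0g/L), at the last blood sample analysis" governs further courses. The follow-up rule applies after completion. Different thresholds for different decisions are not a contradiction.
- **A fully depleted patient counts as recovered at 20 cells/mcL.** Setting values to the quantification limit is a convention for analyses, summaries and plots (SAP Section 12), and the figure of 20 comes from the B-cell AUC exclusion in Section 12.2. Neither governs a follow-up decision.
- **A B-cell count failing both criteria is itself classed as recovered.** It is not. That patient leaves only through the marker reading of *one of them*.

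**Conclusion.** The concern holds as a contradiction within the rule. On the wording alone, every value between the LLN and half of baseline meets start and stop together, and overlap survives each combination of readings in Step 3. Separately, the marker reading lets IgM or IgG end mandated monitoring of B cells that fail both criteria. This is more than missing detail, because a site that follows the text literally can discharge a patient on the result that triggered monitoring.

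The consequence is limited to who stays in the mandated 8-weekly checks and when the follow-up behind the second study report closes. The planned B-cell analyses are not affected. The number of patients cannot be computed, because no LLN and no baseline distribution is given. The IgG ranges rest on assumed LLNs; the overlap itself does not. The point should be corrected, but it does not threaten the trial's primary conclusions.

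**What to change.** The sponsor and DSMB should reconcile the start and stop wording in every place listed above, in both documents, so that no value meets both. The amended text should state:

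1. whether *one of them* refers to a marker or to a criterion;
2. whether recovery of one marker ends follow-up of the others;
3. how the DSMB sentence relates to the fixed 8-weekly rule.

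No threshold or stopping rule is proposed here. That choice belongs to the sponsor and DSMB, who should consider patients whose baseline is already below the LLN.

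The cost is one corrected rule carried through the affected sections and footnotes. Depending on the choice made, some patients may have extra 8-weekly draws, and follow-up, and with it the second study report, may close later.
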